### **12.1.3. Sight Threatening Events**

For the purposes of this study the following ocular adverse events will be reported as serious adverse events:

- Loss of 6 or more lines of vision ( $\geq 30$  letters) from Baseline;
- Endophthalmitis;
- Purulent, infectious conjunctivitis;
- Retinal detachment;
- IOP  $> 35$  mmHg that persists for at least 7 days despite pharmacologic therapy;
- Other significant ocular events per Investigator's discretion

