7. **When a subject cannot read at least 20 letters on the chart at 4.0 meters, the subject is tested at 1.0 meter.** The distance from the subject to the chart should be measured again using the rigid one meter stick. **The distance is measured from the outer canthus to the center of the fourth letter (right eye) or the second letter (left eye) of the third line of the chart.** The spherical correction in the trial frame should be changed by **adding +0.75** to correct for the closer test distance. The subject may fixate eccentrically or turn or shake his/her head to improve visual acuity. Particular care should be taken to make sure the subject does not move forward when testing at 1 meter. The subject should be reminded to blink.
8. The examiner should not tell the subject if a letter was identified correctly. The subject may be encouraged by neutral comments, such as “good”, “next”, and “OK.”
9. The examiner should not stand close to the chart during testing. Attention should be focused on the subject and data collection form. If the subject has difficulty locating the next line to read, the examiner may go up to the chart and point briefly to the next line to be read, but then must move away from the chart.
10. **When 20 or more letters are read at 4 meters the visual acuity score for that eye is recorded as the number of letters correct at 4 meters plus 30.** The subject **gets credit for the thirty 1 meter letters** even though they did not have to read them. Otherwise, the visual acuity score is the number of letters read correctly at 1.0 meter plus the number, if any, read at 4 meters. If no letters are read correctly at either 4 meters or 1 meter, then the visual acuity score is recorded as 0.

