#### **21.4.3.1.7. Testing for Count Finger Vision, Hand Motion Vision and Light Perception/No Light Perception Vision**

If the subject's visual acuity is so poor that he/she cannot read any chart letters when tested at one meter then the subject's ability to count fingers, detect hand motion, or have light perception should be evaluated.

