#### **21.4.3.1.7.3. Testing for Light Perception/No Light Perception Vision**

Light perception should be tested with an indirect ophthalmoscope in a darkened room. The fellow eye should be completely patched and covered by the subject's hand. The indirect ophthalmoscope light should be in focus at 1 meter with the rheostat set at maximum voltage. From that distance the beam should be directed in and out of the subject's eye at least four times, and the subject should be asked to respond when he/she sees the light. If the examiner is convinced that the subject perceives the light, vision should be recorded as "light perception," if not, vision should be recorded as "no light perception."

4M Refraction Protocol Summary							
Refraction Distance	Check Sphere First then Power			Check Cylinder Axis		Sphere "Refinement"	
	Power (a)	Increment	Axis (b)	Power (c)	Increment	Power (d)	Increment
20/10 – 20/80 (4 meters)	+.50 -.50	+.50 -.50	.25 JCC	.25 JCC	+.25 -.25	+.25 -.25	+.25 -.25
20/100 – 20/160 (4 meters)	+1.00 -1.00	+1.00 -1.00	.50 JCC	.50 JCC	+.50 -.50	+.50 -.50	+.50 -.50
20/200 – 20/400 (1 meter)	+2.00 -2.00	+2.00 -2.00	1.00 JCC	1.00 JCC	+1.00 -1.00	+1.00 -1.00	+1.00 -1.00
<20/400 (1.0 meters) sequence refraction a-d	+2.00 -2.00	+2.00 -2.00	No cylinder test required			No refinement required	

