## **8.3. Best-Corrected Visual Acuity (BCVA)**

BCVA and change from baseline in BCVA at Month 12 and Study Exit visit will be summarized and listed.

Subjects with improvement or worsening of at least 5 letters, 10 letters, or 15 letters in study eye at Month 12 visit will be tabulated, as well as subjects maintained BCVA within 5 letters of change in study eye.

Subjects with any BCVA score of 0 after baseline will be listed.

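### SAP 8.3 defines maintained BCVA from letters alone, so an eye starting at 0 to 4 letters that declines off the chart counts as maintained; the 5-letter boundary is also left undefined

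*SAP*

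**What the plan says.** SAP 8.3 sets up the category table in one sentence. It opens with the change groups: "Subjects with improvement or worsening of at least 5 letters, 10 letters, or 15 letters in study eye at Month 12 visit". The second half of the sentence brings in the stable group; the subjects just named "will be tabulated, as well as subjects maintained BCVA within 5 letters of change in study eye". The same section summarises and lists BCVA and its change from baseline at Month 12 and at study exit, and adds a listing: "Subjects with any BCVA score of 0 after baseline will be listed". SAP 4.2.3 defines change as the post-baseline score minus the baseline score, and SAP Table 3 gives BCVA in ETDRS letters, with 5 letters to a line.

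Protocol 21.4.3.1.6 sets the bottom of the scale: "If no letters are read correctly at either 4 meters or 1 meter, then the visual acuity score is recorded as 0". Protocol 21.4.3.1.7 then continues below the chart for an eye that reads nothing at one metre: "the subject's ability to count fingers, detect hand motion, or have light perception should be evaluated". The subsections give pass rules for each level and end with no light perception as a recorded result. The SAP does not mention these levels.

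The first entry in the sight-threatening list in Protocol 12.1.3, repeated in SAP 4.4.1.2.1, is "Loss of 6 or more lines of vision", set at 30 letters or more from baseline. The list ends with an entry left to the investigator's discretion.

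**The concern.** Long-term safety is the only objective, and change in BCVA is a named safety parameter. The row that readers will take as reassurance is the one for maintained vision. Two features of its definition matter.

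First, the letter score stops at 0, while vision can still fall from count fingers to no light perception. A rule based only on letters cannot see that fall, and it sees almost nothing of a fall from 1 to 4 letters to no light perception. Both would appear as stability.

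Second, the maintained category and the smallest change categories meet at 5 letters, and the SAP does not say on which side exactly 5 belongs. Letters are whole numbers and 5 letters is one line, so the value can occur. Two programmers could produce different safety tables from the same data.

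**Working it through.** The plan states no figure for this point, so there is none to reproduce. The check applies the stated rules.

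**Floor.** Inputs: a score of 0 when no letters are read (Protocol 21.4.3.1.6); change = post-baseline score - baseline score (SAP 4.2.3); worsening rows at losses of 5, 10 and 15 letters or more (SAP 8.3); sight-threatening loss of 30 letters or more (Protocol 12.1.3, SAP 4.4.1.2.1). The final score is 0 in every row below.

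| Baseline | Final vision | Letter change | Category in SAP 8.3 | 30-letter item |
|---|---|---|---|---|
| Count fingers (0) | No light perception | 0 - 0 = 0 | Maintained | Not met |
| 4 letters | No light perception | 0 - 4 = -4 | Maintained | Not met |
| 5 letters | No light perception | 0 - 5 = -5 | Worse by ≥5; also maintained if 5 is included | Not met |
| 25 letters | No light perception | 0 - 25 = -25 | Worse by ≥5, ≥10 and ≥15 | Not met |
| 30 letters | No light perception | 0 - 30 = -30 | Worse by ≥5, ≥10 and ≥15 | Met |

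In general, the largest possible loss from a baseline of b letters is b. No worsening row can be reached when b is below 5, and the 30-letter item cannot be reached when b is below 30. The eyes wrongly shown as maintained on any reading are therefore those with a baseline of 0 to 4 letters. The eligibility criteria in Protocol 8.1 and 8.2 set no minimum BCVA, so such eyes are not excluded by this protocol.

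**Boundary.** Every whole-letter change from -100 to +100 was placed in the categories under both readings of 'within 5':

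- Including 5 (|change| ≤ 5): -5 and +5 fall both in maintained and in a change row. No other value overlaps with maintained, and none is left out.
- Excluding 5 (|change| < 5): maintained, improved by ≥5 and worsened by ≥5 neither overlap nor leave a gap.

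**Possible size of the boundary effect.** The documents give no SD or mean for BCVA change, so both are assumptions here. For a normal change rounded to whole letters, with mean 0 and SD σ:

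P(|change| = 5) = Φ(5.5/σ) - Φ(4.5/σ) + Φ(-4.5/σ) - Φ(-5.5/σ)

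- σ = 5: 9.7%; 60 × 0.0968 = 5.8 subjects
- σ = 10: 7.0%; 60 × 0.0704 = 4.2 subjects
- σ = 20: 3.9%; 60 × 0.0387 = 2.3 subjects

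Moving the mean to -3 or +3 gives 9.6% at σ = 5 and 3.8% at σ = 20. The 60 is the adjusted sample size in SAP 3.3. These counts also assume that all 60 have Month 12 data, and they apply only if 5 is included in maintained. Otherwise the number in two rows is 0.

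**The case against.** The case against has real force, and four stronger claims that a reader might infer are not supported.

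- *The plan counts a 5-letter change twice.* It does not say so. Excluding 5 is a natural complement to the change rows and removes the overlap. The defect is an undefined boundary.
- *Rows that sum to more than 100% prove an error.* They do not. The 5-, 10- and 15-letter rows are nested, so an eye losing 16 letters is in three rows by design.
- *Eyes with the poorest vision cannot register in the table.* Most can. A fall from 25 letters to 0 enters all three worsening rows. Only baselines of 0 to 4 letters are missed.
- *The listing of 0 scores hides whether the 0 is new.* At letter level it does not, because SAP 8.3 also lists change from baseline. What stays hidden is movement among the off-chart levels, since no listing is said to carry them.

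There are also other routes to detection. Protocol 12.1.1 treats a significant change from baseline as an adverse event; Protocol 12.1.2 makes an event serious if sight is in immediate danger, whatever the letter score; Protocol 14.6 lists clinically significant BCVA changes; and SAP 8.1 tabulates serious and ocular events. These stand, but they depend largely on investigator judgement, Protocol 14.6 gives no BCVA threshold for clinical significance, and none of them corrects the maintained count.

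Finally, no document shows that an eye near or below the bottom of the chart enrolled. Subjects needed investigator-judged benefit from earlier treatment, and other significant vision-compromising disease of the study eye was excluded. The affected group may be empty.

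**Conclusion.** The floor problem holds on any reading. By the plan's own scoring and change rules, an eye with a baseline of 0 to 4 letters that declines to, or within, the off-chart range is tabulated as maintained and cannot be tabulated as worse. The 30-letter item cannot catch it, although the judgement-based serious-event criteria can. Its size is unknown and may be nil.

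The boundary problem is an ambiguity to settle before tabulation. It produces double counting only if 5 is included. The 2 to 6 of 60 worked out above is an illustration resting on assumed SDs of 20 down to 5, complete Month 12 data and the inclusive reading. SAP 7.1 plans for non-completers and SAP 6.2.1 imputes nothing, so the Month 12 denominator may be below 60.

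The study tests no hypothesis, so no test, power or error rate is affected. What is at stake is whether one row of a descriptive safety table means what its label says.

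**What to change.** In SAP 8.3:

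1. Define maintained as a change of -4 to +4 letters. With the existing change rows this leaves no overlap and no gap. SAP 7.6 already writes its exposure bands with explicit bounds of this kind.
2. Add a row for off-chart decline: any fall from a letter score to count fingers, hand motion, light perception or no light perception, or any step down among these. Count it as worsening and exclude those eyes from maintained. Item 1 alone does not cure the floor, because count fingers to no light perception is still a change of 0.
3. Show the off-chart level at baseline and post-baseline in the listing of 0 scores.

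Keep the new row in the BCVA table. It comes from examination data and should not be mixed into the sight-threatening summary, which reports investigator-recorded adverse events.

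The cost is SAP wording, one table row and added listing columns. No new examination is needed, since the protocol already tests these levels. The row does depend on the levels being available from the eCRF or source; the SAP defines the analysed variable in letters only, so this must be checked first. The maintained percentage may become slightly less favourable.

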## **8.4. Intraocular Pressure (IOP)**

IOP, change from baseline in IOP at the Study Exit visit, and change after injection in IOP will be summarized.

Subjects with elevated IOP reported as an AE will be tabulated. Subjects with any increase of  $\geq 10$  mmHg in IOP from baseline at any post-baseline visit, or after injection will be tabulated and listed. In addition, Subjects with IOP of at least 25, 30, or 35 mmHg at any post-baseline visit will be summarized.

### **8.5. Indirect Ophthalmoscopy**

For retina, macula, choroid, and optic nerve, shift from baseline in status (Normal or Abnormal) will be summarized at study exit visit and shift after injection will be summarized by injection visit. Subjects with any change from normal at baseline to abnormal in status after baseline will be listed.

For phakic lens only, shift from baseline in presence of cataract (Yes or No) at study exit visit will be summarized. Subjects with no cataract presence at baseline to cataract presence after baseline, if any, will be listed.

### **8.6. Treatment Exposure**

The exposure to DE-109 will be evaluated by descriptive summaries of number of injections during the study, time to first injection, and study days on the drug.

### **8.7. Use of Rescue Therapy**

Subjects who take any medication qualified as rescue therapy, or who have vitrectomy procedures in study eye will be listed. The rescue rate in SPRING study will be calculated. Time to first rescue from Day 1 for rescued subjects will be summarized descriptively. Subgroup analysis of rescue rate will be performed by rescue status in SAKURA study, and received injection or not in SPRING study.

### **8.8. Slit-lamp Biomicroscopy**

Only subjects who are under US Amendment 01 have slit-lamp biomicroscopy assessments. However, none of those subjects have slit-lamp biomicroscopy records at baseline since all of them entered the amendment after day 1. Taking this fact into consideration, all the slit-lamp biomicroscopy parameters (Lid Hyperemia, Lid Edema, Conjunctival Hyperemia, Chemosis, Corneal Edema, Conjunctival Discharge Exudate, Anterior Chamber Flare, Pupil, Lashes, Ocular Motility, Iris, Vitreous Cell Count and Anterior Chamber Cells) will be presented only in listings.

### **8.9. Central Retinal Thickness**

Since central retinal thickness assessment is at investigator's discretion and is only for subjects under US Amendment 01, only a few records were collected. Therefore, subjects with central retinal thickness records will simply be listed by type of OCT machine.

